Protocol Name:	Investigational Study of the Ekso Bionics Powered Exoskeleton for High-Dosage Use by Individuals with Spinal Cord Injury in a Non-Clinical Environment
	Principal Investigator:	[name], Sr. Controls Engineer
	Primary Contact Name/Contact Info:	[name], Sr. Controls Engineer [contact] [contact]
	Date Revised:	9/28/2015
	Study Number:	13098-01

Investigational Study of the Ekso Bionics Powered Exoskeleton for High-Dosage Use by Individuals with Spinal Cord Injury Walking in a Non-Clinical Environment

1. Investigator

Facility PI: [name], Sr. Controls Engineer, Ekso Bionics

2. Date Revised

September 28, 2015

3. Objectives

- 3.1 To determine the physiological effects of high-dosage use of the Ekso device over a 12- 36-month period.
- 3.2 To documents the quality of life benefits of using an Ekso device in a non-clinical setting.
- 3.3 To define the safety and efficacy of using the device in a home environment.
- 3.4 To determine the safety and efficacy of a non-medical professional spotting the subject.
- 3.5 To determine inclusion/exclusion criteria for an Ekso Bionics device used in a home setting.

4. Background

The incidence of spinal cord injury is estimated at 1.5-5.3 million worldwide.⁽¹⁾ "Will I walk again?" is often cited as one of the more common questions, with the decreased ability to walk as one of the most difficult challenges to live with.^(2,3) Over the last 10 years more research has focused on the ability for the spinal cord to "heal" itself, i.e. undergo plasticity,^(4,5) by task-specific, high-

	Protocol Name:	Investigational Study of the Ekso Bionics Powered Exoskeleton for High-Dosage Use by Individuals with Spinal Cord Injury in a Non-Clinical Environment
	Principal Investigator:	[name], Sr. Controls Engineer
	Primary Contact Name/Contact Info:	[name], Sr. Controls Engineer [contact] [contact]
	Date Revised:	9/28/2015
	Study Number:	13098-01

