Primary Contact Name/Contact Info:	[name], Sr. Controls Engineer [contact] [contact]
Date Revised:	9/28/2015
Study Number:	13098-01

6.4.9. Helping the subject safely perform simple daily tasks inaccessible to the subject while in the device (e.g., bend down to get a plate from a cabinet or open a door)

6.5. Ekso Bionics will:

6.5.1. Evaluate the efficacy of a spotter in a home environment.
6.5.2. Evaluate the safety of using the device in a home environment.

6.6. After initial training at either Ekso Bionics or at the participant's home, a follow-up evaluation device operation may be conducted either in-person or by video at weeks 3 and 7. Review meetings will be held every three months from the time the device is delivered to the subject's home (or more frequently) to evaluate safety and efficacy. Information gathered from the study and status meetings will be used by Ekso Bionics to further the product development. Information may also be used by Ekso Bionics Marketing to determine the most appropriate market for the device and by Clinicians to aid in training future clinical staff.

Schedule of study measure.

	Baseline	3 months	6 months	9 months	12 months	Every 6 months after
Device measures (6.1.1 – 6.1.4)		✓	✓	✓	✓	✓
Physiological measures (6.1.5 – 6.1.7)	✓	✓	✓	✓	✓	✓
Frequency of secondary health conditions (6.1.8)	✓	✓	✓	✓	✓	✓

	Protocol Name:	Investigational Study of the Ekso Bionics Powered Exoskeleton for High-Dosage Use by Individuals with Spinal Cord Injury in a Non-Clinical Environment				
	Principal Investigator:	[name], Sr. Controls Engineer				
	Primary Contact Name/Contact Info:	[name], Sr. Controls Engineer [contact] [contact]				
	Date Revised:	9/28/2015				
	Study Number:	13098-01				

Quality of Life measures (6.1.9)	√	√	√	√	√	√
Functional ability (6.1.10)	√	√	√	√	√	√
Pain (6.1.11)	√	√	√	√	√	√
Spasticity (6.1.12)	√	√	√	√	√	√
Strength testing (6.1.13)	√	√	√	√	√	√
Bone Density (6.1.14)	√				√	

7. Inclusion and Exclusion Criteria

7.1. Subject Inclusion Criteria:

Participants must have a spinal cord injury between C7-L3 resulting in motor paralysis.

Participants must meet each of the remaining criteria:

7.1.1. be an experienced user of the Ekso device with a minimum of 20 hours and no more than 50 hours of device use and require no greater than minimal assist (support of up to 25% body weight) for safe and consistent walking.

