7.1.1.1 no more than 2 episodes of balance loss per 1 hour training session that require no more than moderate assistance (support of 26% to 50% of body weight)

7.1.1.2 participants with more than 50 hours of device experience must agree to a 1 month period of non-use prior to acquisition of baseline measures

7.1.2. be between 18-65 years of age.

7.1.3. be able to physically fit into the exoskeleton device.

7.1.4. be able to tolerate upright standing for up to 60 minutes.

	Protocol Name:	Investigational Study of the Ekso Bionics Powered Exoskeleton for High-Dosage Use by Individuals with Spinal Cord Injury in a Non-Clinical Environment
	Principal Investigator:	[name], Sr. Controls Engineer
	Primary Contact Name/Contact Info:	[name], Sr. Controls Engineer [contact] [contact]
	Date Revised:	9/28/2015
	Study Number:	13098-01

7.1.5. have sufficient joint range of motion to fit safely within Ekso:
 Hip flexion contracture ≤ 150 ; knee flexion contracture ≤ 100 ;
 ankle dorsiflexion to neutral with no more than 10° of knee flexion.

7.1.6. have sufficient upper body strength to balance themselves with two arms

7.1.7. be fluent in English

7.2. Subject Exclusion Criteria:

7.2.1. Height below 60 inches or above 76 inches or with physical characteristics incompatible with device and testing procedure.

7.2.2. Weight above 220 lbs.

7.2.3. Lower extremity joint contractures that exceed device capacity for safe use.

7.2.4. Any medical issue that precludes full weight bearing and ambulation (e.g. osteoporosis that prevents safe standing, orthopedic injuries, pain, severe spasticity)

7.2.5. Skin integrity issues that would prevent wearing the device.

7.2.6. Cognitive and/or communicative disability inappropriate for testing as determined by Ekso Bionics clinician. Subjects must be able to follow directions well and demonstrate learning capability.

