16.1. The risk of falling: This could be caused by loss of control of the ambulation activity by the participant or spotter as well as malfunction of the Ekso device itself. The risk of falling will be minimized by having a trained spotter with the subject at all times. The risk of falling is further mitigated by allowing only very experienced subjects who have been approved by the Ekso Bionics Clinical Team walk in the device during the study. This risk is similar to any gait therapy in which subjects with lower extremity disorders are standing and walking.

16.2. Risk of exceeding subject range of motion: This would be caused if the Ekso moved the subject beyond their normal range of

Protocol Name:	Investigational Study of the Ekso Bionics Powered Exoskeleton for High-Dosage Use by Individuals with Spinal Cord Injury in a Non-Clinical Environment
Principal Investigator:	[name], Sr. Controls Engineer
Primary Contact Name/Contact Info:	[name], Sr. Controls Engineer [contact] [contact]
Date Revised:	9/28/2015
Study Number:	13098-01

motion, resulting in a strain, sprain and/or fracture. This risk is mitigated by mechanical hard stops that prevent the device from exceeding a normal human range of motion even in the event of a failure in the electrical or software systems. Software systems are also in place to further reduce range of motion to improve fit and comfort for subjects during walking. Subjects will be evaluated by trained Ekso Bionics clinicians who will eliminate any subjects from participation if they cannot meet the required range of motion.

16.3. Discomfort, skin pressure/friction, bruising, pain, or unusual swelling caused by the exoskeleton which has the potential to lead to skin breakdown or abrasions. All locations where the subject contacts the exoskeleton are padded to prevent bruising or skin irritations. Also all pinch points are covered and protected from catching either skin or clothing. Adjustments to the harness placement and additional padding will be assessed to decrease the risk of skin breakdown as well.

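### Objective 3.5 promises to determine home-use entry criteria, but enrolment only inside preset limits can at most suggest, descriptively, that a limit is too loose

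*Protocol*

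**What the plan says.** Section 3.5 gives as an objective "To determine inclusion/exclusion criteria for an Ekso Bionics device used in a home setting".

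Section 7.1 sets the subject criteria before enrolment starts. It opens with "Participants must have a spinal cord injury between C7-L3 resulting in motor paralysis" and continues "Participants must meet each of the remaining criteria". Among those that follow are "be an experienced user of the Ekso device with a minimum of 20 hours and no more than 50 hours of device use", no more than minimal assistance when walking, "no more than 2 episodes of balance loss per 1 hour training session", age 18 to 65, and tolerance of up to 60 minutes' standing. Section 7.2 excludes on size ("Height below 60 inches or above 76 inches", and weight above 220 lbs), contracture and several medical grounds. Sections 7.3 and 7.4 do the same for spotters, and the environmental requirements do so for the place of use.

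Under 8.2 the sponsor's clinical team decides eligibility from a clinical evaluation, a home-site evaluation, spotter interviews and the subject's experience and capability. Section 16.1 lists as a protection against falls "allowing only very experienced subjects who have been approved by the Ekso Bionics Clinical Team walk in the device during the study".

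On device hours, 7.1.1.2 adds that "participants with more than 50 hours of device experience must agree to a 1 month period of non-use prior to acquisition of baseline measures".

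Section 9 sets 2 to 12 subjects. Section 12.2.1 provides for periodic evaluations against the general criteria, and 7.2.9 allows exclusion for conditions that arise after the start.

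**The concern.** To determine an entry limit, one needs some information from both sides of it, or at least a plan for learning from people near it. Here every subject, spotter and home is screened to lie inside. No cohort beyond the limits, stepwise relaxation or follow-up of people screened out is described, and no measure in 6.1 or endpoint in 11.1 is tied to objective 3.5.

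At stake is what may be concluded. The objective's wording would let criteria that were assumptions at the start be read as results at the end. Section 6.6 allows the study's information to be used in product development and in choosing the market for the device, so the difference has practical weight.

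**Working it through.** The protocol gives no sample-size or precision figure for this objective, so there is nothing of its own to reproduce. The check is mainly one of design logic, with some arithmetic on what 2 to 12 subjects can show.

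**What each source of information can tell**

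- *People beyond a limit at entry.* None are enrolled, so the number is 0 at any sample size. Nothing can be learned about whether a looser limit would do.
- *Enrolled subjects who run into difficulty.* These can suggest that a limit is too loose. The routes are 12.2.1 (periodic evaluation against the criteria), 7.2.9 (conditions arising on study), 12.3 (observed balance, stability and use) and 11.1 (closing interviews or questionnaires).
- *Subjects who drift past a limit during 12 to 36 months.* The evaluations in 12.2.1 may pick them up. But they met the criteria at entry, so they say little about admitting someone who does not, and the protocol does not say what follows from such a finding.
- *Device hours.* Section 7.1.1 sets a ceiling of 50 hours; 7.1.1.2 admits people above it after a month without use. If the second passage governs, both sides of this one limit could be observed. No comparison by hours is described, the month of non-use would differ along with the hours, and the 20-hour floor stays unexamined.

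**What is recorded**

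Section 6.1 already collects some values that bear on Section 7: pain (6.1.11), spasticity (6.1.12), motor scores (6.1.13) and bone density (6.1.14). Device hours at entry, assistance level, balance losses per session, injury level, contracture and standing tolerance are not listed there, nor are reasons for screen failure.

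**How much 2 to 12 subjects can show inside the limits**

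Inputs: n = 2 and n = 12 (Section 9). The protocol defines no failure and gives no failure rate. I take failure to mean any safety or capability problem that leads to stopping, and the rates below are assumptions.

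1. Exact one-sided 95% upper bound with no failures, 1 − 0.05^(1/n):
   - n = 12: 1 − 0.05^(1/12) = 0.221
   - n = 2: 1 − 0.05^(1/2) = 0.776
2. Chance of seeing at least one failure, 1 − (1 − p)^n:

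| Assumed true rate p | n = 12 | n = 2 |
|---|---|---|
| 5% | 46% | 10% |
| 10% | 72% | 19% |
| 20% | 93% | 36% |

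3. Linking failure to one entry characteristic, 12 subjects split 6 and 6, Fisher's exact test, two-sided 0.05:
   - 0/6 against 4/6: p = 0.061
   - 0/6 against 5/6: p = 0.015
   - Power at assumed rates of 10% and 50%: 6%; 10% and 60%: 14%; 10% and 80%: 44%

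So a single limit that is too loose may well show itself as a problem in someone among 12 subjects, but the study could rarely attribute that problem to a particular criterion by a formal comparison.

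**The case against.** The strongest reply is that the study is not silent on where limits should lie. The entry ranges are broad, spotters and homes vary, follow-up runs for 12 to 36 months, and 12.2.1 brings clinicians back to the criteria periodically. Experience inside the limits can therefore point to narrower ones. This stands. A reader might infer that the study can say nothing about the limits; the documents do not support that, because tightening remains open.

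It is also fair that the criteria are not wholly fixed. Device hours are contradictory, and 7.2.3 and 7.2.6 rest on clinical judgement. Some criterion-related values are already scheduled, and the appendix forms are listed only by title, so their content cannot be judged.

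The bounds of 22.1% and 77.6% hold for any result with no events at these sizes, and the protocol calls itself exploratory and a pilot. That too is right: the figures show how little can be read from the data, and are not in themselves a fault.

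A reader might further infer that the sponsor will present its starting criteria as findings. Nothing says so. Section 6.6 says only that information may be used in considering the market. The wording of 3.5 leaves that reading open but does not announce it.

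What the reply does not meet is the one-sidedness. Calling the study exploratory does not give it observations beyond the limits, and an analysis plan cannot recover entry values or screening reasons that were never recorded.

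**Conclusion.** Objective 3.5 claims more than the design can deliver. The study can suggest, descriptively, that a limit is too loose; it cannot show that an entry limit is too strict or could be widened, because nobody beyond it is enrolled. Device hours above 50 are the partial exception, and there the protocol contradicts itself. The conclusion about widening follows from the eligibility text alone and needs no assumed rate. The statement that evidence for tightening is weak rests on 2 to 12 subjects and on the assumed failure rates and definition given above.

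This is a minor point about one of five objectives, worth acting on because the correction is cheap and changes what may be concluded.

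**What to change.** - Restate 3.5 as: to assess whether subjects and spotters who meet the Section 7 criteria can use the device safely at home, and to describe the entry characteristics of those who cannot. Add that the study cannot support widening any criterion.
- Reconcile 7.1.1 with 7.1.1.2 on device use above 50 hours. No view is taken here on which should stand.
- Record in the study data each subject's entry value on the Section 7 criteria that 6.1 does not cover: device hours, assistance level, balance losses per session, injury level, contracture and standing tolerance.
- For each person screened under 8.2 but not enrolled, log the criterion that failed.
- Name the 12.2.1 evaluations as the on-study source for this objective.
- Tabulate entry values descriptively by reason for stopping. Keep safety and capability reasons (7.2.9, 11.2.4, 11.2.5) apart from personal choice (11.2.1), equipment faults (11.2.3) and 21-day non-use for unrelated reasons (11.4), since a pooled table would mix in stops that have nothing to do with any criterion. Sections 11.2.2 and 11.2.6 cover mixed causes, so classify those stops by the recorded reason.

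The cost is a narrower claim, a screening log, a few extra recorded values and one descriptive table. Enrolment and the entry limits need not change, apart from the reconciliation on device hours.

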This is a 36 month exploratory Investigational Study compliant with the NSF Human Subjects regulations (45 CFR 690) trialing a new device for the SCI populations to aid in ambulatory function in a home setting. Ekso Bionics will enable up to twelve (12) subjects with SCI to use an Ekso device in their home for a 12-month period. Qualified subjects will help Ekso Bionics determine the practical use of the device in the home environment and will enable Ekso Bionics to gather data to develop a device for use in a home environment. The study will require a trained spotter to be present at all times that the device is being used. The study will also evaluate the effectiveness of a non-medically licensed spotter to assist the subject.

6.1. The study will measure and evaluate the following to enable Ekso Bionics to determine the physiological benefits of high-dosage use of the device in the home. Baseline measures will be recorded at the beginning of the study and reassessed a minimum of every three months over a twelve month period (+/- 2 weeks) and every 6 months after (+/- 2 weeks). The metrics include:

- 6.1.1. The number of Ekso sessions completed
- 6.1.2. Number of steps taken in device (per week, average per session, whole time)
- 6.1.3. Time spent walking in device (per week, average per session, whole time)

	Protocol Name:	Investigational Study of the Ekso Bionics Powered Exoskeleton for High-Dosage Use by Individuals with Spinal Cord Injury in a Non-Clinical Environment
	Principal Investigator:	[name], Sr. Controls Engineer
	Primary Contact Name/Contact Info:	[name], Sr. Controls Engineer [contact] [contact]
	Date Revised:	9/28/2015
	Study Number:	13098-01

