Protocol Name:	Investigational Study of the Ekso Bionics Powered Exoskeleton for High-Dosage Use by Individuals with Spinal Cord Injury in a Non-Clinical Environment
Principal Investigator:	[name], Sr. Controls Engineer
Primary Contact Name/Contact Info:	[name], Sr. Controls Engineer [contact] [contact]
Date Revised:	9/28/2015
Study Number:	13098-01

The Investigational study will take place over the course of 36 months. Each subject will be evaluated for a minimum of 12 months during the 36 month period.

If at any point during the study, the subject must take a break from regular walking for medical or personal reasons, if the break is less than 2 month, they will be able to restart the study by notifying the principal investigator of the break and resuming use. If the break is greater than 2 months, the subject will need to be re-evaluated by an Ekso Bionics physical therapist to restart the study. In the case of a break of more than 2 months, the study clock will be considered "paused" at this point and the next evaluation after the initial re-evaluation will be 3 months later (+/- 2 weeks) if in the first year of the study and 6 months (+/- 2 weeks) after beyond the first year of the study.

11. Endpoints

11.1. At the conclusion of the 12-month training period, final measurements will be taken, both the subject and the non-clinical spotter will be interviewed or a questionnaire (Appendix C) will be provided to obtain information that will assist Ekso Bionics with further development of the device. Measurements will continue to be collected every 6 months for up to the conclusion of the study or the subject terminates his/her enrollment.

11.2. Sessions will be ended for any of the following reasons:

11.2.1. Subject decides to stop participation in the study at any time and for any reason.

11.2.2. An Ekso Bionics staff member stops the subject from taking part in this study at any time if he believes it is in the subject's best interest or if the subject does not follow the study protocol.

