11.2.3. Equipment is operating inconsistently or is deemed unsafe

Protocol Name:	Investigational Study of the Ekso Bionics Powered Exoskeleton for High-Dosage Use by Individuals with Spinal Cord Injury in a Non-Clinical Environment
Principal Investigator:	[name], Sr. Controls Engineer
Primary Contact Name/Contact Info:	[name], Sr. Controls Engineer [contact] [contact]
Date Revised:	9/28/2015
Study Number:	13098-01

11.2.4. A therapist/researcher involved feels that the subject's performance or continued usage places them at risk for injury.

11.2.5. The subject is experiencing any adverse medical condition as evaluated by the subject, clinician or spotters.

11.2.6. The subject or assistants to the subject (spotter or otherwise), deliberately or not, does not follow the study protocol or uses or permits use of the device in an unsafe manner.

11.3. If the subject, deliberately or not, does not follow the study protocol or uses or permits use of the device in an unsafe manner, the device may be returned to Ekso Bionics without financial reconciliation to the subject.

11.4. If the subject does not walk in the Ekso for a period of more than 21 days for any reason, they will be withdrawn from the investigation.

11.4.1. If the subject wishes to resume participation in the study, additional training of the subject and baseline assessments may be necessary.

12. Procedures Involved in the Human Research

12.1. The study is designed to enable Ekso Bionics to evaluate the high-dosage use of a robotic exoskeleton in the home environment by persons with spinal cord injury. The study is based on the existing Ekso device. Features will include devices and controls to emulate proper gait training, stability and walking for common daily function. The device will not allow all daily functions including bending over, squatting, toilet use, climbing up or down stairs or ramps, side stepping or backward stepping.

Protocol Name:	Investigational Study of the Ekso Bionics Powered Exoskeleton for High-Dosage Use by Individuals with Spinal Cord Injury in a Non-Clinical Environment
Principal Investigator:	[name], Sr. Controls Engineer
Primary Contact Name/Contact Info:	[name], Sr. Controls Engineer [contact] [contact]
Date Revised:	9/28/2015
Study Number:	13098-01

12.2. Since the study involves periodic observation and data collection for evaluation by Ekso Bionics clinical, engineering and marketing personnel, the testing procedures includes:

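### The protocol gives two different periods of device use (12 months, and up to 36), and 11.4 confines month-18 and later data to subjects who keep walking

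*Protocol*

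**What the plan says.** Two sets of passages bear on how long a subject uses the device.

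**Passages that read as 12 months.** Section 6: "Ekso Bionics will enable up to twelve (12) subjects with SCI to use an Ekso device in their home for a 12-month period". Section 11.1: "At the conclusion of the 12-month training period, final measurements will be taken".

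**Passages that presuppose longer use.**
- Objective 3.1: "To determine the physiological effects of high-dosage use of the Ekso device over a 12- 36-month period".
- Section 6.1: measures are "reassessed a minimum of every three months over a twelve month period (+/- 2 weeks) and every 6 months after (+/- 2 weeks". In the schedule table, the row beginning "Device measures (6.1.1 – 6.1.4" is ticked in the column for 6-monthly visits after month 12. These measures are sessions, steps, walking time and time in each walking mode.
- Section 10, which sets the evaluation interval after a long break from walking, has a separate provision for breaks beyond the first year.
- Section 7.3.7 requires spotters to be available for the whole study, and Section 10 says "The Investigational study will take place over the course of 36 months".

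**Rules on not walking.** Section 11.4 says that a subject who "does not walk in the Ekso for a period of more than 21 days for any reason, they will be withdrawn from the investigation". Section 11.4.1 allows a return, possibly with retraining and new baseline assessments. Section 10 handles breaks differently. Under 2 months the subject notifies the principal investigator and resumes; over 2 months the subject is re-evaluated and the study clock is paused.

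**The concern.** The length of the intervention is the exposure named in the first objective, and the protocol states it in two ways. That alone calls for reconciliation.

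The 21-day rule gives the ambiguity a statistical consequence. A subject who uses the device for the period named in Section 6 and then stops leaves the study under 11.4 before any later visit falls due. Everyone observed at month 18 or later is then, by construction, someone who kept access to a device and a spotter and chose to keep walking. Such subjects may well differ from the others in tolerance, perceived benefit and health. With 2 to 12 subjects (Section 9) and no comparison group described, that selection cannot be separated from an effect of longer use. A summary of month-18 and later results could then be read as the effect of 12 to 36 months of use in the enrolled subjects, when it describes only the continuers.

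**Working it through.** There is no power or sample-size figure to reproduce; the check is on the calendar.

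**Inputs.** Period of use of 12 months (Section 6). Non-use limit of more than 21 days (11.4). Later visits every 6 months, each within 2 weeks either side (6.1). Study length of 36 months (Sections 6 and 10). Assumptions: 1 month = 365.25 / 12 = 30.44 days, and the 36 months run from the first enrolment.

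**When 11.4 applies to a subject who ends use at month 12.**
- Last use: 12 × 30.44 = day 365.
- First day with more than 21 days of non-use: 365 + 22 = day 387.
- Opening of the month-18 window: 18 × 30.44 − 14 = day 534.
- Gap: 534 − 387 = 147 days, or 21 weeks.

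If use instead runs to the end of the month-12 visit window, the limit is passed at 365 + 14 + 22 = day 401, and the gap is 534 − 401 = 133 days, or 19 weeks. Either way the subject is withdrawn well before the first later visit, and the month-24, 30 and 36 visits are later still.

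**How many later visits exist at all.** Available follow-up is 36 minus the study month of enrolment:

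| Enrolled at study month | Follow-up available (months) | Possible visits after month 12 |
|---|---|---|
| 0 | 36 | 18, 24, 30, 36 |
| 6 | 30 | 18, 24, 30 |
| 12 | 24 | 18, 24 |
| 18 | 18 | 18 |
| 24 | 12 | none |

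Four later visits is therefore a maximum, reached only by subjects enrolled at the outset.

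**Section 10 against 11.4.** Two months is about 61 days. For a break of 22 to about 61 days, Section 10 lets the subject resume on notification, while 11.4 has already withdrawn them. For a longer break, Section 10 pauses the clock and 11.4 withdraws. Both cannot apply. For a subject who does not resume walking, the choice makes no difference to the data: Section 10 times the next evaluation from a re-evaluation to restart, which never happens.

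**The case against.** The best reply is that 12 months was meant as a minimum and that Section 6 is loosely worded. Much of this stands. Section 10 says "Each subject will be evaluated for a minimum of 12 months during the 36 month period", objective 3.1 starts its range at 12 months, and the schedule table, the break provision beyond the first year and 7.3.7 all anticipate continued walking. Under 13.1.1, subjects who buy a device keep it at the end of the study. A reader might infer from Section 6 and 11.1 that subjects must stop at month 12, so that the long-term part of 3.1 can yield no data. The documents do not support that: no passage directs a stop or a return of the device at month 12, and the return provision in 11.3 concerns breach of protocol or unsafe use.

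The reply does not remove the point. The minimum in Section 10 is one of evaluation, not of use, and neither Section 6 nor 11.1 words 12 months as a minimum. Even on that reading, 11.4 still removes anyone who stops after month 12.

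Two further objections are fair. First, 11.1 ends measurement at study conclusion or when the subject terminates enrolment, and does not mention 11.4; that measurement ends on withdrawal from the investigation is the natural reading, but an inference. Second, 11.4.1 and Section 10 offer a way back, though only to those who resume. A reader might also fault the plan for not testing whether 12-month changes persist after use stops. No objective in Section 3 asks that, so it is not a gap in this plan.

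**Conclusion.** The concern holds in a limited form. The period of use is stated inconsistently, 11.4 conflicts with Section 10, and under 11.4 month-18 and later data are confined to continuing walkers. A subject who stops at month 12 is withdrawn 19 to 21 weeks before the first later visit could take place, and so contributes to none of the later visits (at most four).

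This rests on 11.4 being applied as written and on withdrawal ending assessment. How many subjects would stop at month 12 is not given in the protocol and cannot be derived from it, so the number lost is unknown; the upper limit on those who could contribute later data is the 12 enrolled. The 12-month results are not affected by this point, nor is bone density, which is scheduled only at baseline and month 12. The matter should be corrected because it bears directly on objective 3.1 and costs little, but it does not invalidate the study.

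**What to change.** 1. Reconcile Section 6 and 11.1 with 3.1, the schedule table, Section 10 and 11.4, so that the protocol states one planned period of device use and one status for subjects who stop after completing 12 months. Which period and which non-use rule apply is the sponsor's decision.
2. Whatever the device-use status, continue the 6-monthly assessments already scheduled that do not need a walking session, in consenting subjects who completed 12 months. These are 6.1.6 to 6.1.10, the between-session pain data set in 6.1.11, 6.1.12 and 6.1.13. Leave out the device measures (6.1.1 to 6.1.4), exertion (6.1.5) and within-session pain, which have no meaning without a session.
3. At each later visit, record whether the subject is still using the device and, if not, the stop date.
4. Report month-18 and later results by use status, with the number in each group, and not as the effect of 12 to 36 months of use in all subjects.

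The cost is protocol wording and a few assessment visits for subjects who no longer walk in the device, on dates the schedule already contains. Follow-up of those who stop depends on their willingness, so some selection will remain, but it will be visible.
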